#### 5.4.7 BMI

$$\text{BMI (kg/m}^2\text{)} = \text{Body weight (kg)}/\{\text{Body height (m)}\}^2$$

It will be rounded off the second decimal place and reported the value to the first decimal place.

#### 5.4.8 Medical history and Adverse events

All medical history and adverse events will be coded from the actual term using the MedDRA version 20.0 or the later version.

#### 5.4.9 Adverse reactions

Adverse reactions are defined as adverse events that are determined to have a “reasonably possible” causal relationship to the study drug.

#### 5.4.10 Duration of the AE and time to the AE

Duration of the AE and time to the AE occurrence from start of study medication will be calculated and presented in days, where AE duration = AE stop date – AE start date + 1 and the time to the AE occurrence = AE start date – first DB dose date + 1.

#### 5.4.11 Prior and Concomitant medications

All prior and concomitant medications will be coded using the WHO drug dictionary (WHO Herbal Dictionary) (Version SEP 2017).

#### 5.4.12 Duration of exposure and Cumulative Dosing Count

The duration of exposure is calculated as the total number of days that the subject has been treated with double-blind study medication—that is, from the treatment start date to the date of their EOT/withdrawal visit. For subjects lost to follow up, the treatment end date is taken to be the date of their last visit. Interruptions, compliance, and dose changes are not taken into account for duration of exposure.

Duration of exposure (days) = date of end of treatment visit – date of first dose of double-blinded study medication; Cumulative Dosing days= Duration of exposure – number of days subject miss the medication

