4.5 Withdrawal of individual subjects

4.5.1 Discontinuation from study treatment

Investigators may choose to temporarily or permanently discontinue study treatment for any reason, including AEs or tolerability.

Study

drug administration can be interrupted and reinitiated following up to 7 days of discontinuation. An unscheduled study visit can be used to reassess subject's symptoms and willingness to reinitiate study drug. In these circumstances, the patient will complete the dosing through the remainder of the planned study duration. If treatment is discontinued, and patient is not willing to resume study medication, every effort should be made to continue the subject on study, e.g., attending study visits and carrying out study procedures through to the final visit. For subjects decline continuing on the study, see Section 4.5.2.

The suspension interval (start and end dates of suspension) and reason for suspending treatment must be recorded in source documents and the electronic Data Collection Form (eCRF).

Subjects who become pregnant during the study should be withdrawn from study treatment. Also see Section 8.9 for necessary documentation and procedures for following up with the subject.

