5.2.3 Double-blind Treatment (Visits 3 through 7)

Subjects who successfully complete Screening and Placebo Run-in periods will return to the clinic for the Randomization visit on Day 1 and participate in the Double-blind Treatment period.

Inclusion and exclusion criteria will be reviewed to confirm eligibility prior to randomization.

Randomized subjects who are withdrawn early from the study should, where possible, complete the procedures scheduled for the EOT (Week 12) visit as soon as possible after withdrawal. Every effort should be made to maintain randomized subjects on study, even in cases where treatment has been discontinued.

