#### 5.4.13 Treatment Compliance

Compliance with double-blind study medication—based on the drug accountability data—will be calculated as the number of days subjects take study medication divided by the duration of exposure in days, expressed as a percentage.

Study medication compliance will be calculated as follows:

$$\frac{\text{Cumulative Dosing days}}{(\text{date of end of treatment visit} - \text{date of randomization})} \times 100\%$$

The subjects should take one dose daily per protocol.

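### SAP 5.4.12 describes duration of exposure as days treated but counts to the EOT visit, so women who stop drug and stay in the study are recorded as exposed for about 84 days

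*SAP*

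**What the plan says.** SAP 5.4.12 gives the meaning of the variable first: "The duration of exposure is calculated as the total number of days that the subject has been treated with double-blind study medication". The same sentence then sets the span as running "from the treatment start date to the date of their EOT/withdrawal visit", and the formula follows that span: "Duration of exposure (days) = date of end of treatment visit – date of first dose of double-blinded study medication". For women lost to follow-up, the last visit stands in for the end of treatment. The section adds: "Interruptions, compliance, and dose changes are not taken into account for duration of exposure". It also derives cumulative dosing days, which is duration of exposure less the days on which medication was missed.

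SAP 7.6 assigns duration of exposure to Table 14.1.5 in the safety population. SAP 5.4.13 describes compliance as days on which medication was taken, "divided by the duration of exposure in days, expressed as a percentage". The displayed formula there starts its denominator at randomization instead.

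Protocol 4.5.1 says: "If treatment is discontinued, and patient is not willing to resume study medication, every effort should be made to continue the subject on study". Protocol 5.2.3 repeats the request: "Every effort should be made to maintain randomized subjects on study, even in cases where treatment has been discontinued". In the schedule of assessments and Protocol 5.2.3.5, the EOT visit is Visit 7, at Week 12 (Day 85 ±3) or at early termination. Its footnote and Protocol 4.5.2 tie the early version to leaving the study. No visit is triggered by stopping drug alone.

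**The concern.** The description and the formula agree only for women who take drug up to the EOT visit. The protocol deliberately creates a group for whom they differ: women who stop drug for good and continue to attend. For them the formula returns the length of follow-up under the label of time on treatment.

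A reader of Table 14.1.5 will take it as time on drug when judging adverse events, laboratory values and endometrial findings by dose. The error is always upward, and it grows with the share of an arm that stops and stays. If that share rises with dose, the table hides a difference in actual exposure between arms.

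**Working it through.** **Inputs**
- First double-blind dose: Day 1 (SAP Table 5).
- EOT visit: Day 85, window Day 82 to Day 88 (schedule of assessments).
- Double-blind period: 12 weeks, or 84 days (Protocol synopsis).
- Last dose day L, and share p of an arm that stops drug but stays to EOT: not in the documents, so assumed below.

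**Step 1. The SAP formula for a woman who attends Week 12.** EOT day − first dose day = 85 − 1 = 84 days, which matches the 12-week period. Over the window, 82 − 1 = 81 and 88 − 1 = 87. L does not enter the formula.

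**Step 2. Time on drug.** Last dose day − first dose day + 1 = L − 1 + 1 = L.

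| Last dose day | Days on drug | SAP duration | Excess | Ratio |
|---|---|---|---|---|
| 7 | 7 | 84 | 77 | 12.0 |
| 14 | 14 | 84 | 70 | 6.0 |
| 28 | 28 | 84 | 56 | 3.0 |
| 56 | 56 | 84 | 28 | 1.5 |
| 70 | 70 | 84 | 14 | 1.2 |

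**Step 3. Mean for an arm.** With everyone else at 84 days, true mean = (1 − p) × 84 + p × L, and overstatement = 84 / true mean − 1. For p = 10% and L = 28: 0.90 × 84 + 0.10 × 28 = 78.4 days, and 84 / 78.4 − 1 = 7.1%.

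| Share who stop and stay | L = 14 | L = 28 | L = 42 |
|---|---|---|---|
| 5% | 80.5 days (4.3%) | 81.2 (3.4%) | 81.9 (2.6%) |
| 10% | 77.0 (9.1%) | 78.4 (7.1%) | 79.8 (5.3%) |
| 20% | 70.0 (20.0%) | 72.8 (15.4%) | 75.6 (11.1%) |

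The excess in mean days runs from 84 − 81.9 = 2.1 to 84 − 70.0 = 14.0.

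**Step 4. Whether cumulative dosing days recover the true figure.** This depends on whether days after a permanent stop count as missed, which the SAP does not say. For L = 14:
- Counted as missed: 84 − 70 = 14 dosing days, and compliance is 14/84 = 16.7%.
- Not counted: 84 − 0 = 84 dosing days, and compliance is 84/84 = 100%.

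**Step 5. Effect of a last-dose definition on completers.** Dosing is at bedtime, so the last dose before a Day 85 visit falls on Day 84, and 84 − 1 + 1 = 84. Completers keep the same value; women who stop and stay are corrected.

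**The case against.** The strongest reply is that the SAP discloses its convention. It says that interruptions and compliance are ignored, and it derives a second variable net of missed days. That variable feeds the compliance table, and all administration data are listed by subject.

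This stands in part. Ignoring short gaps is a common choice. But Protocol 4.5.1 separates an interruption with restart (after up to 7 days) from stopping without resuming, and the SAP sentence does not mention the second. Cumulative dosing days give the right answer only on one of two unstated readings (Step 4). Reading the withdrawal visit as withdrawal from treatment does not help either, because no visit is scheduled at that point.

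The reply also limits the consequences. Four stronger readings are tempting, and the documents do not support them:
- **That exposure is a denominator for safety rates.** SAP 7.10.1 counts subjects, SAP 5.3 uses subjects in the treatment group as the default denominator, and no exposure-adjusted rate appears in the visible text.
- **That the per-protocol set is affected.** Protocol 7.3 defines non-compliance from visit to visit, with a redacted threshold, and nothing visible links the whole-period percentage in SAP 5.4.13 to major deviations.
- **That low compliance for an early stopper is an error.** Counting undosed days against the assigned regimen is legitimate. A denominator that ended at the last dose would give a Day 14 stopper 100% and hide non-persistence.
- **That dosing days are left out of every exposure summary.** SAP 7.6 names only duration, but the list of tables is not in the available text.

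Women who leave the study are also largely unaffected, because Protocol 5.2.3 asks for their EOT procedures soon after withdrawal.

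**Conclusion.** The point holds as a definitional error in a reported safety-population variable. The meaning given in SAP 5.4.12 and the formula beside it disagree for any woman who stops drug and stays in the study. Her recorded exposure is about 84 days regardless of her last dose.

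The individual ratios follow from the documents' own dates once a last dose day is assumed. The arm-level range of about 2.6% to 20% rests entirely on assumed shares of 5% to 20% and assumed last doses between Day 14 and Day 42; if few women stop and stay, the effect is small. It is confined to the descriptive exposure summary and to judgements about safety by dose that lean on it. No efficacy test and no subject-count adverse event table changes. This is a minor correction, worth making because it is cheap.

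**What to change.** 1. In SAP 5.4.12, define duration of exposure as last double-blind dose date − first double-blind dose date + 1. Take the last dose date from the most recent dose dates recorded at Visits 4 to 7 and the treatment suspension or discontinuation dates in the eCRF. Use accountability data as support only, since capsule counts need not give a date.
2. State that days after permanent discontinuation count as missed when cumulative dosing days are taken over the planned or EOT span. The span and the missed days must match: for a last dose on Day 14 with no other missed days, 84 − 70 and 14 − 0 both give 14, but subtracting 70 from the new 14-day duration would not.
3. In SAP 5.4.13, keep the compliance denominator as the span to the EOT visit so that non-persistence stays visible. The text there now points to duration of exposure, so it must be reworded once that variable changes.
4. Use one start date in 5.4.13. The text implies first dose and the formula uses randomization.

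The cost is SAP wording and a small change to derivation programs. The dates named above are already collected, and values for completers do not change.

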#### 5.4.13 Treatment Compliance

Compliance with double-blind study medication—based on the drug accountability data—will be calculated as the number of days subjects take study medication divided by the duration of exposure in days, expressed as a percentage.

Study medication compliance will be calculated as follows:

$$\frac{\text{Cumulative Dosing days}}{(\text{date of end of treatment visit} - \text{date of randomization})} \times 100\%$$

The subjects should take one dose daily per protocol.

#### 5.4.14 The Estimated Glomerular Filtration Rate (eGFR)

$eGFR = 141 \times \min(S_{Cr}/\kappa, 1)^\alpha \times \max(S_{Cr}/\kappa, 1)^{-1.209} \times 0.993^{\text{Age}} \times 1.018 \text{ [if female]} \times 1.159 \text{ [if Black]}$

$S_{Cr}$  (standardized serum creatinine) = mg/dL

$\kappa$  = 0.7 (females) or 0.9 (males)

$\alpha$  = -0.329 (females) or -0.411 (males)

min = indicates the minimum of  $S_{Cr}/\kappa$  or 1

max = indicates the maximum of  $S_{Cr}/\kappa$  or 1

Age = years

It will be rounded off the second decimal place and reported the value to the first decimal place.

#### 5.4.15 MENQOL scores deriving

The MENQOL is self-administered and consists of a total of 29 items in a Likert-scale format. Each item assesses the impact of one of four domains of menopausal symptoms, as experienced over the last month:

- vasomotor (items 1–3)
- psychosocial (items 4–10)
- physical (items 11–26)

- sexual (items 27–29)

Items pertaining to a specific symptom are rated as present or not present, and if present, how bothersome on a zero (not bothersome) to six (extremely bothersome) scale. Means are computed for each subscale by dividing the sum of the domain's items by the number of items within that domain. Non-endorsement of an item is scored a "1" and endorsement a "2," plus the number of the particular rating, so that the possible score on any item ranges from one to eight. (Hilditch JR, et al. 1996) Total MENQOL score will be calculated as the average of each domain score.

[figure not shown]
#### 5.4.16 Lab values below/above the limit of quantitation deriving

The lab values below the limit of quantification (BLQ) are collected in the form like "< 2" in the clinical data base. In this case the numeric value of the lab is missing value. The cut-off value '2' will be used to impute the missing value for this case. Similarly, for the lab values above the limit of quantification, the cut-off value will be used for the numeric value of the lab.

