2.2.5 Safety assessments

- Physical examination (including breast safety evaluation)
- Vital signs (blood pressure, pulse, and tympanic body temperature)
- ECG parameters (including cardiac intervals: heart rate, PR, QRS, QT, and QTcF)
- Clinical laboratory assessments (hematology, biochemistry, coagulation, and urinalysis)
- Reproductive hormones (luteinizing hormone [LH], follicle stimulating hormone [FSH], and estradiol [E2])
- Adverse events (AEs)
- Endometrial safety (endometrial thickness, as measured by transvaginal ultrasound, and incidence of endometrial hyperplasia, as measured by endometrial biopsy)
- Depression and anxiety symptoms as measured by 8-item Patient Health Questionnaire (PHQ-8) and 7-Item Generalized Anxiety Disorder questionnaire (GAD7), respectively

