**Table 6 Imputation of lab values below/above the limit of quantification**

Lab Test	Characteristic value	Derived Numeric value	
Bilirubin	<2	2	
Direct Bilirubin	<2	2	
Estradiol	<61	61	
Luteinizing Hormone	<0.1	0.1	
Specific Gravity	>1.045	1.045	

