### 7.10 Safety Assessments

The safety evaluation will be purely descriptive using descriptive statistics (N, mean, SD, median minimum and maximum) or frequency tables where appropriate using SAF population, unless otherwise specified. No imputation will be made in case of missing values.

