### 7.10.2 Laboratory Tests

For all continuous laboratory parameters, the lab values and change from baseline to post baseline visits are summarized by treatment group and visit.

For all discrete laboratory parameters, the lab values are summarized with count and percentage by treatment group and visit. (Table 14.3.2.1, Table 14.3.2.2, Table 14.3.2.3, Table 14.3.2.4, Table 14.3.2.5)

The lab tables will be generated for each Lab categories (Hematology, Coagulation, Biochemistry and Hormones and Urinalysis).

All laboratory data will be listed with clinically relevant values flagged (L=Lower than lower limit of normal range or H=Higher than upper limit of normal range).

In addition, following clinical relevant ranges (and flags) will also be considered for summary table. The count and percent of subjects meeting the criteria will be presented. (Table 14.3.2.6)

- ALT  $\geq 3 \times$  Upper Limit of Normal Range (ULN), 5 $\times$  ULN, 8 $\times$  ULN, 10 $\times$  ULN
- AST and/or ALT  $\geq 3 \times$  ULN, 5 $\times$  ULN, 8 $\times$  ULN, 10 $\times$  ULN
- AST and/or ALT  $\geq 3 \times$  ULN with Total bilirubin  $\geq 2 \times$  ULN
- Total bilirubin  $\geq 2 \times$  ULN
- Creatinine  $\geq 2 \times$  ULN

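### Replacing estradiol results below 61 with 61 pulls the tabulated change from baseline toward zero, and the laboratory section plans no count of the substituted values

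*SAP*

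**What the plan says.** The protocol names estradiol as a safety assessment (section 2.2.5): "Reproductive hormones (luteinizing hormone [LH], follicle stimulating hormone [FSH], and estradiol [E2".

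SAP 5.4.16 explains that a below-limit result is stored as text and says of it: "In this case the numeric value of the lab is missing value". The limit is then substituted; the example given is "The cut-off value '2' will be used to impute the missing value for this case". The estradiol row of Table 6 reads "Estradiol <61 61", with no unit.

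The substituted values flow into the laboratory summaries. SAP 7.10.2 states: "For all continuous laboratory parameters, the lab values and change from baseline to post baseline visits are summarized by treatment group and visit". Its tables are made by category, including "Biochemistry and Hormones and Urinalysis". SAP 7.10 sets the statistics: "N, mean, SD, median minimum and maximum".

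SAP 7.10 also rules out imputing missing values in the safety summaries. Section 5.4.16 calls the below-limit value missing and imputes it.

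The text available describes no count of below-limit results, no shift table between below-limit and quantifiable, no censored-data summary and no alternative substitute value. The table list in SAP section 11 is not part of that text.

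**The concern.** The substitute is the largest value a below-limit result could have, and it is then averaged as if it had been measured. A woman below 61 at both visits contributes a change of exactly 0, whatever happened to her estradiol. A woman who crosses the limit contributes only the part of her rise above 61.

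The trial enrols postmenopausal women, some after bilateral salpingo-oophorectomy, so below-limit results are plausible, and Table 6 has a row for them. If they are common, the mean change in the hormone table cannot separate no change from not measurable. The reading of a named safety assessment is at stake. No efficacy conclusion is.

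**Working it through.** **Inputs from the documents.** Limit L = 61 and substitute 61 (SAP Table 6); levels and changes by arm and visit (SAP 7.10.2); mean, SD, median, minimum and maximum (SAP 7.10). The estradiol distribution, the below-limit share and the unit of 61 are not given.

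**Step 1: reproduce Table 6.** Using the cut-off as the value gives bilirubin 2, direct bilirubin 2, estradiol 61, luteinizing hormone 0.1 and specific gravity 1.045 (an upper limit). All five rows match.

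**Step 2: direction, with no distribution assumed.** The rule replaces X by g(X) = max(X, 61). This function never decreases and has slope 0 or 1. Hence:
- mean of g(X) ≥ mean of X;
- SD of g(X) ≤ SD of X;
- |g(Y) − g(X)| ≤ |Y − X| for every woman, whether she rises or falls.

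A numerical check on 2,000 random data sets found no violation.

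**Step 3: single women.**

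| True values | True change | Recorded change |
|---|---|---|
| 20 to 40 | +20 | 61 − 61 = 0 |
| 20 to 60 | +40 | 61 − 61 = 0 |
| 20 to 80 | +60 | 80 − 61 = +19 |
| 50 to 100 | +50 | 100 − 61 = +39 |
| 90 to 30 | −60 | 61 − 90 = −29 |
| 70 to 90 | +20 | +20 (unaffected) |

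**Step 4: group means under an assumed model.** Take X log-normal with log-mean μ and log-SD s. For a baseline below-limit share p, μ = ln 61 − s·z(p), where z(p) is the standard normal quantile. Then

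E[g(X)] = 61·Φ((ln 61 − μ)/s) + exp(μ + s²/2)·Φ((μ + s² − ln 61)/s).

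A true doubling adds ln 2 to μ. The mean change is the difference of the two expectations, so it does not depend on the within-woman correlation.

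Worked line for p = 0.90, s = 0.5:
- μ = 4.111 − 0.5 × 1.2816 = 3.470, so the true baseline mean is exp(3.595) = 36.4, and a doubling adds 36.4.
- Tabulated baseline: 61 × 0.900 + 36.4 × 0.217 = 62.8.
- Tabulated after doubling: 61 × 0.458 + 72.9 × 0.727 = 80.9.
- Tabulated rise: 80.9 − 62.8 = 18.1, about half of 36.4.

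All lines, s = 0.5, true doubling (true, then tabulated):

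| Below limit at baseline | Baseline mean | Baseline SD | Mean rise | Understated by |
|---|---|---|---|---|
| 25% | 96.8, 100.5 | 51.6, 48.1 | 96.8, 93.4 | 3.5% |
| 50% | 69.1, 78.3 | 36.8, 29.9 | 69.1, 60.9 | 12% |
| 70% | 53.2, 68.8 | 28.3, 18.8 | 53.2, 40.2 | 24% |
| 90% | 36.4, 62.8 | 19.4, 8.1 | 36.4, 18.1 | 50% |
| 95% | 30.4, 61.8 | 16.2, 5.0 | 30.4, 11.1 | 63% |

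The log-SD matters little. Over values from 0.5 to 0.8, the understatement is 3 to 4%, 11 to 12%, 23 to 25%, 50 to 51% and 63 to 65% on the same five lines. Smaller rises lose more: for a 1.5-fold rise at s = 0.5, the loss is 6% at 25% below the limit and 63% at 90%.

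**Step 5: SD of change.** Step 2 does not cover this quantity. With an assumed baseline-to-post correlation of 0.7, s = 0.5 and a doubling, simulation gives a true SD of change of 55.7 against 58.5 under the rule at 50% below the limit, and 24.6 against 22.5 at 95%. It can move either way.

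**The case against.** Four points on the other side have force.

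**The size is assumed.** A reader might infer that nearly all results are below 61, because the women are postmenopausal. That is plausible, but the documents give no share, no distribution and no unit. With few below-limit results the loss is a few per cent. This stands: direction is certain, size is not.

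**The planned table gives partial warning.** A reader might infer that the rule hides heavy censoring entirely. It does not. If more than half the values are below the limit, the median prints as 61, the value shown in Table 6. The minimum is less informative, since a single below-limit result is enough to make it 61. The share in each arm still cannot be read off. All laboratory data are also listed by subject, although the SAP does not say whether the listing keeps `<61`.

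**Precision.** A reader might infer that the change from baseline will look falsely precise. Only the SD of levels must shrink; the SD of change need not (Step 5).

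**Consequence.** SAP 7.10 says: "The safety evaluation will be purely descriptive using descriptive statistics". No test, efficacy endpoint or error rate uses estradiol in the visible text. Endometrial safety is assessed directly, by centrally read ultrasound (SAP 7.10.7.1) and adjudicated biopsy (7.10.7.2). A reader might infer a threat to the endometrial safety conclusion, and the documents do not support that. However, descriptive tables are the whole of the planned safety evaluation, so no other analysis corrects a distorted mean change.

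The blinded data review (SAP 7.1) may add handling rules, but none for below-limit results is stated.

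**Conclusion.** The point holds as a low-cost improvement to a descriptive safety table. The stated rule raises the mean estradiol level, shrinks the SD of levels, and moves each affected woman's change toward zero, for rises and falls alike. None of this rests on a distribution. It follows that a group mean change is understated when changes run mainly in one direction.

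The size rests on the log-normal assumption and on a below-limit share that the documents do not state. For a doubling it runs from about 4% (25% below the limit) to about 50% (90% below). The documents do not support a claim that the estradiol table will be uninformative, that its changes will look too precise, or that any efficacy or endometrial result is affected.

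The wording of SAP 5.4.16 and 7.10 on imputing missing values conflicts and needs reconciling whatever the below-limit share.

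**What to change.** In SAP 5.4.16 and 7.10.2, for estradiol and any other Table 6 analyte with below-limit results:

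- Report n (%) below the limit by arm and visit.
- Add a shift table from baseline to Week 12/EOT, below limit versus quantifiable.
- Show the median and minimum as below the limit (`<61` for estradiol) where that applies.
- When half or more of the values are below the limit, base the reading on these displays and not on the mean change.
- Footnote any mean or SD that contains substituted values.
- State the unit of the estradiol limit in Table 6.
- Reconcile 7.10 with 5.4.16, for instance by excepting results outside the quantification limits from the statement on missing values.

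A fixed percentage trigger and a censored log-normal model are not needed for a descriptive table. Another constant would not cure the problem: in the 90% scenario, half the limit (30.5) gives a rise of 31.7 against a true 36.5 in the simulation.

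The cost is some SAP wording and one extra table from data already collected. The drawback is less emphasis on a simple mean change for estradiol.
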